**- The primary and secondary endpoints:**

The primary endpoint is the percentage of patients with peripheral sensory neuropathy grade  $\geq 2$ , the variation of 12-item neurotoxicity questionnaire (Ntx-12) total score and the variation in grades of mucositis. The secondary endpoint is the change in the serum concentrations of the measured biological markers.

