## **C. Assessment of Chemotherapy induced toxicities**

### **I. Clinical assessment of oxaliplatin induced peripheral neuropathy**

Clinical assessment of oxaliplatin induced neuropathy will be done through:

- The assessment of the severity of neuropathic pain through brief pain inventory short form "BPI-SF" worst item (16). Severity of neuropathic pain will be assessed at baseline and by the end of every two chemotherapy cycles.
- The implication of National Cancer Institute Common Terminology Criteria for Adverse Events (NCI-CTCAE, Version 5, 2017) for grading of neuropathy (17) at baseline and by the end of every two chemotherapy cycles.
- The use of Neurotoxicity- 12 item questionnaire score (Ntx-12) from the validated Functional Assessment of Cancer Therapy/Gynecologic Oncology Group "FACT/GOG-Ntx-12" (18) at baseline and by the end of every two chemotherapy cycles).

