**- Sample size calculation:**

According to the results of previous studies, the total number of subjects required to detect the effect of neuro-protective drugs in patients received neuro-toxic chemotherapy was 41 patients with 5% significance, 80% statistical power and an attrition of 15 % (19, 20). In this context, during the current study, a total sample size of 41 patients in both arms will be sufficient to detect the effect. Assuming that the attrition rate will be 15 %, the initial sample size will be 48 patients in both arms with 24 patients in each arm.

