**- Statistical analysis:**

- The collected data will be tabulated using Microsoft® Office Excel, 2019 (Microsoft Corporation).
- The statistical analysis will be carried out using SPSS statistical package version 26.0 (IBM corporation software group, USA).
- Data will be tested for normality using Shapiro-Wilk test or Kolmogorov–Smirnov test.
- Parametric data will be analyzed using Paired and un-Paired *t*-test to compare the means within the same group and to compare the means of the two groups respectively.
- Non- Parametric data will be analyzed using Mann Whitney U test to compare the means within the same group and to compare the means between groups.
- Categorical data will be analyzed using Chi-Square test.
- Fisher’s exact test will be used to analyses the reported adverse effects.
- Correlation between variables will be assessed using Pearson or Spearman correlation coefficient which appropriate.
- Data will be expressed as the mean  $\pm$  SD, medians, range, number and percent as appropriate.
- The significance level will be set at  $p \leq 0.05$ .

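### Three outcomes form one primary endpoint at p ≤ 0.05 with no success rule, order, alpha control or primary time: about 8–14% error if any one suffices, power below 80% if all must succeed

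*Combined protocol and SAP*

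**What the plan says.** The section on primary and secondary endpoints uses the singular but lists three outcomes. It opens "The primary endpoint is the percentage of patients with peripheral sensory neuropathy grade" ≥ 2 and continues with "the variation of 12-item neurotoxicity questionnaire (Ntx-12) total score and the variation in grades of mucositis". It gives no analysis time and does not define *variation*.

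The toxicity assessment section (parts C.I and C.II) schedules all three at baseline and after each pair of cycles; for neuropathy the text is "for grading of neuropathy (17) at baseline and by the end of every two chemotherapy cycles". With the 12 cycles in the study design section, that makes six post-baseline assessments.

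The statistical analysis section assigns tests by type of data:
- Parametric data get paired and unpaired t-tests, "to compare the means within the same group and to compare the means of the two groups respectively". Non-parametric data get Mann-Whitney.
- For the rest, "Categorical data will be analyzed using Chi-Square test", while Fisher's exact test is kept for reported adverse effects.
- "The significance level will be set at" p ≤ 0.05, without distinction between primary and other tests.

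The sample size section cites 5% significance with "80% statistical power and an attrition of 15" percent, and concludes that "a total sample size of 41 patients in both arms will be sufficient to detect the effect". It does not say which outcome that effect concerns.

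**The concern.** The plan does not define a positive trial. The word *and* in the endpoint sentence joins a list; it is not a success rule. Three readings are open: any one outcome suffices, all three are needed, or neuropathy and mucositis are separate claims, matching the two targets named in the Aim of the work.

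The stated 5% and 80% do not both survive under any of these readings without further rules. The first and third allow a false-positive rate above 5%. The second protects the error rate but lowers the power.

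Other choices are open too: the visit, whether grade ≥ 2 means at or by that visit, whether *variation* is a change from baseline or a worst grade, and whether a within-group or a between-group test decides. Neuropathy and mucositis are both graded by CTCAE, so they could fall under the chi-square rule for categorical data or the Fisher rule for adverse effects. If these choices are made after results by group are known, the nominal p-value no longer describes the procedure.

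**Working it through.** **Inputs from the plan.** Three primary outcomes; p ≤ 0.05; 5% significance, 80% power and 15% attrition; 41 patients inflated to 48; 12 cycles with assessment every two.

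**Assumptions, because the plan is silent.** Two-sided tests, correlations between outcomes, and power per outcome. Correlated cases use a multivariate normal simulation of the test statistics.

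**1. The plan's own figure.** 41 × 1.15 = 47.15, rounded up to 48; 41 / 0.85 = 48.2. So 48 follows from 41 to within one patient. The 41 itself cannot be rebuilt, because no outcome, effect size, SD or event rate is given.

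**2. Any one of three, no true effects, one time each.** If independent, 1 − 0.95³ = 0.1426. Otherwise the error is P(at least one |Z| > 1.960). Joint power for all three, with 80% each, uses Z with mean 1.960 + 0.842 = 2.802 and asks that every Z exceed 1.960. If independent, this is 0.8³ = 0.512.

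| Common correlation | Any-one error | All-three power (80% each) |
|---|---|---|
| 0 | 14.3% | 51% |
| 0.3 | 13.6% | 57% |
| 0.5 | 12.5% | 61% |
| 0.7 | 10.9% | 66% |
| 0.8 | 9.8% | 69% |
| 0.9 | 8.4% | 72% |

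**3. A more realistic pattern.** Neuropathy grade and Ntx-12 both measure neurotoxicity, while mucositis is a different toxicity. With (correlation of the two neuropathy outcomes, correlation of mucositis with each), the any-one error is 13.6% at (0.5, 0), 12.8% at (0.7, 0.2), 11.7% at (0.9, 0) and 11.4% at (0.9, 0.3).

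**4. Separate claims.** For the two neuropathy outcomes alone, the any-one error is 1 − 0.95² = 9.75% if independent, about 9.0% at correlation 0.5 and 7.0% at 0.9.

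**5. All three required, unequal power.** Joint power cannot exceed the lowest single-outcome power. If the binary outcome has 50% and the others 80%, it is 0.5 × 0.8 × 0.8 = 32% if independent, 38% at correlation 0.3 and 42% at 0.5. About 50% is plausible for the binary outcome: with 41 evaluable patients split 20/21, the exact power of the uncorrected chi-square test is 52–53% for assumed rates of 60% and 30%, and 52–56% for 50% and 20%. It is about 78% for 60% and 20%.

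**6. Size of the binary test.** At 20 and 21 patients, summing binomial probabilities over the rejected tables gives the uncorrected chi-square test a true size of 5.1–6.0% for common rates of 20–50%. Steps 2 to 4 are therefore approximate for that outcome.

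**7. Power under the two candidate rules (80% each before adjustment).**

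| Rule | Power per outcome |
|---|---|
| Holm, all three effects true, correlation 0–0.5 | 73–75% |
| Holm, two effects true | 69–70% |
| Holm, one effect true | 66% |
| Fixed sequence, first / second / third, correlation 0–0.5 | 80% / 64–69% / 51–61% |

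With no true effects, Holm's overall error is 3.0–4.9% across correlations 0–0.9.

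**The case against.** The best defence is that *and* means all three, in which case the error is not inflated. Or the two aims are separate clinical questions, and whether those must share one alpha is partly convention. Both points stand as possible readings, but neither is stated. The first leaves the 80% unsupported for the joint claim; the second still leaves two neuropathy outcomes uncontrolled. It is also fair that the plan is not silent on tests: it assigns them by data type after a normality check. What is missing is which comparison and which test decide each primary outcome.

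A reader might infer more than the documents support:
- *The trial's error rate is 14.3%.* That is the independence case under the any-one reading, and the two neuropathy outcomes are probably correlated.
- *The trial's power is 51–61%.* That requires all three to succeed, 80% power for every outcome and correlations of 0–0.5. The plan gives none of these, and the figure could be higher or lower.
- *Both failings occur together.* They belong to alternative readings.
- *Testing at every visit gives 60% error.* With 3 × 6 = 18 tests, 1 − 0.95¹⁸ = 60%, but only if all are independent, which repeated visits are not. Choosing among visits would raise the error by an amount that cannot be calculated from the documents.

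**Conclusion.** The concern holds and should be corrected before the analysis. Under the any-one reading, the chance of at least one false primary finding is about 8–14% at a single time, and about 11–14% under the more realistic correlations. Under separate claims it is about 7–10% for neuropathy. Under the all-three reading the error is at most 5%, but joint power is 51–72% if every outcome has 80% power, and lower otherwise. That the stated 5% and 80% are not tied to a defined conclusion does not depend on the assumed correlations; the sizes do. All figures also assume valid randomisation and complete data.

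**What to change.** Amend the endpoint and statistical analysis sections before outcome data are examined by group. The plan specifies a placebo but does not describe blinding, so this is a safer milestone than unblinding. If group results have already been seen, report the choice as made afterwards.

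1. For each primary outcome, name one analysis time (for example the end of cycle 12; for grade ≥ 2, state whether *at* or *by* that time). Define *variation* as a between-group comparison of change from baseline or of worst grade. Name one between-group test, and state whether chi-square or Fisher's exact test applies to the CTCAE-graded outcomes. Fisher's exact test avoids the slight size excess in step 6, but it is conservative and costs some power.
2. State one rule holding overall two-sided error at 0.05. Preferred text: *The three primary outcomes will be tested by the Holm procedure (ordered p-values against 0.0167, 0.025 and 0.05); benefit will be claimed only for outcomes rejected.* This suits the equal standing of neuropathy and mucositis in the Aim of the work. A fixed sequence, in a stated order and stopping at the first p > 0.05, is an acceptable alternative.
3. Report other visits, within-group tests, biomarkers and correlations as supportive.

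**Cost.** The change is wording only, and the planned 48 patients suffice for error control. They do not keep 80% power per outcome (step 7), so the 80% in the sample size section should be restated for the chosen rule.

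If the sponsor wants to restore 80% under Holm, and 41 evaluable patients give 80% unadjusted, about 46–47 evaluable are needed when all three effects exist and correlations are 0–0.5. With only one true effect the figure is 41 × [(2.394 + 0.842) / 2.802]² = 54.7, or about 55.

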**- Sample size calculation:**

According to the results of previous studies, the total number of subjects required to detect the effect of neuro-protective drugs in patients received neuro-toxic chemotherapy was 41 patients with 5% significance, 80% statistical power and an attrition of 15 % (19, 20). In this context, during the current study, a total sample size of 41 patients in both arms will be sufficient to detect the effect. Assuming that the attrition rate will be 15 %, the initial sample size will be 48 patients in both arms with 24 patients in each arm.

**- Statistical analysis:**

- The collected data will be tabulated using Microsoft® Office Excel, 2019 (Microsoft Corporation).
- The statistical analysis will be carried out using SPSS statistical package version 26.0 (IBM corporation software group, USA).
- Data will be tested for normality using Shapiro-Wilk test or Kolmogorov–Smirnov test.
- Parametric data will be analyzed using Paired and un-Paired *t*-test to compare the means within the same group and to compare the means of the two groups respectively.
- Non- Parametric data will be analyzed using Mann Whitney U test to compare the means within the same group and to compare the means between groups.
- Categorical data will be analyzed using Chi-Square test.
- Fisher’s exact test will be used to analyses the reported adverse effects.
- Correlation between variables will be assessed using Pearson or Spearman correlation coefficient which appropriate.
- Data will be expressed as the mean  $\pm$  SD, medians, range, number and percent as appropriate.
- The significance level will be set at  $p \leq 0.05$ .

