**Document Date: October 12, 2022**

## **Introduction**

Colorectal cancer (CRC) is the third most commonly diagnosed cancer in recent years, and the second leading cause of cancer death globally. In 2020, CRC accounts for 10% of global cancer incidence and 9.4% of cancer deaths, just lower than lung cancer. The global number of new CRC cases is predicted to reach 3.2 million in 2040 (1, 2).

Oxaliplatin is a third-generation platinum-based chemotherapy drug that is considered a key drug in treatment of colorectal cancer (3). The most reported adverse effect of oxaliplatin is neurotoxicity. Oxaliplatin induces two forms of peripheral sensory neuropathy. The first is transient, acute neuropathy usually resolves spontaneously within days. The second form is chronic cumulative poorly reversible peripheral neuropathy that worsens with the repetition of chemotherapy cycles (4).

Although a number of interventions have been implicated, none of them can be recommended for clinical use (5). This therapeutic failure reflects poor understanding of the real mechanism of oxaliplatin-induced neuropathy (6). However, oxidative stress is identified to be one of the main bio-molecular dysfunctions in this neuropathy (7).

This oxidative stress can trigger inflammatory reaction which in turn up-regulates the expression of pro-inflammatory cytokines like tumor necrosis factor- $\alpha$  (TNF- $\alpha$ ), interleukin-1 $\beta$  (IL-1 $\beta$ ), and interleukin-6 (IL-6), which has been well demonstrated to play an important role in the establishment and maintenance of the spinal cord sensitization, resulting in hyperalgesia, and finally inducing neuropathic pain (8). Neurotensin (NT) is an endogenous neuropeptide involved in modulation of pain signal transmission and perception (9, 10). There is a significant increase in NT level in rats treated with oxaliplatin (11).

Intestinal mucositis, or damage to the intestinal mucosa, is a major contributor to the reduced quality of life, decreased survival rates, and early onset of death observed in patients with certain chemotherapeutic agents (12). Citrulline is an amino acid mainly produced by enterocytes of the small bowel. Decreased levels of plasma citrulline are correlated with significant epithelial small bowel loss (13).

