## Patients and Methods

### **- Study design and treatment protocol:**

This study will be a randomized placebo controlled parallel study. Forty-eight eligible patients with stage II and stage III colorectal cancer will be scheduled to receive 12 cycles of folinic acid, fluorouracil and oxaliplatin (FOLFOX6 regimen). Patients will be recruited from the Oncology Department, Tanta University Hospital, Tanta, Egypt. Staging will be done according to the American Joint Committee on Cancer 7th edition staging. The patients will be randomized using according to the days of hospital admission into two groups:

**Group I (control group; n=24)** which will receive 12 cycles of FOLFOX-6 regimen plus placebo tablets twice daily.

The chemotherapy cycles will be received every 2 weeks and will be as follows:

**Day 1:** Oxaliplatin 85 mg/m^2 intravenous infusion in 250-500 mL 5% dextrose solution and leucovorin 400 mg/m^2 intravenous infusion in 5% dextrose solution both were given over 120 minutes at the same time in separate bags using a Y-line access, followed by 5-fluorouracil 400 mg/m^2 intravenous bolus given over 2-4 minutes, followed by 5-fluorouracil 2400 mg/m^2 intravenous infusion in 1000 mL 0.9% Sodium Chloride solution as a 46-hour infusion.

Additionally, Intravenous 5-HT3 antagonist plus pantoprazole will be administered to all participants before each cycle as prophylactic therapy against chemotherapy induced nausea, vomiting and mucositis. Furthermore, all participants will be submitted to complete blood count analysis before each chemotherapy cycle.

**Group II (Pentoxifylline group; n=24)** which will receive FOLFOX-6 regimen in addition to pentoxifylline 400 mg twice daily.

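### Ntx-12 is scheduled seven times, but the plan names no time point, no baseline adjustment and no repeated-measures analysis for it

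*Combined protocol and SAP*

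**What the plan says.** The study design section has patients "scheduled to receive 12 cycles of folinic acid, fluorouracil and oxaliplatin". Section C.I schedules the Ntx-12 questionnaire "at baseline and by the end of every two chemotherapy cycles", and the BPI-SF worst-pain item on the same schedule.

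The endpoint section makes "the variation of 12-item neurotoxicity questionnaire (Ntx-12) total score" one of three primary outcomes. It does not say at which visit, or by what summary, that variation is measured.

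The Statistical analysis section names these comparisons:

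- for normally distributed data, paired t-tests within a group and unpaired t-tests, the latter "to compare the means of the two groups respectively";
- as the rank-based alternative, "Non- Parametric data will be analyzed using Mann Whitney U test";
- for categories, "Categorical data will be analyzed using Chi-Square test", with Fisher's exact test for adverse effects.

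Pearson or Spearman correlations are also listed. There is no baseline-adjusted comparison, no repeated-measures model and no missing-data method.

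Section D (adherence and tolerability) removes from the study anyone who does not take the tablets, misses a follow-up meeting or changes regimen. The sample size section expects 15% attrition.

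**The concern.** The Introduction describes "chronic cumulative poorly reversible peripheral neuropathy that worsens with the repetition of chemotherapy cycles". The assessment schedule suits that course of events, but nothing in the analysis section makes use of it. Because neither the visit nor the summary is fixed, the between-arm test of Ntx-12 can reasonably be read in two ways:

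- **One visit.** An unadjusted comparison at a single visit leaves most of the collected scores unused. A patient who leaves before that visit contributes nothing to it, despite having earlier scores.
- **Every visit.** A separate test at each post-baseline visit uses the scores, but gives up to six chances of a positive result at 0.05, with no rule for choosing among them.

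At stake are precision on the main patient-reported outcome with about 20 evaluable patients per arm, and a primary result that could depend on which visit is reported.

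**Working it through.** **Plan's own figure.** 41 × 1.15 = 47.15, rounded up to 48; 41 / 0.85 = 48.2. The stated 48 is reproduced. Expected completers are 48 × 0.85 = 40.8, about 41, so about 7 patients leave. The 41 itself cannot be rebuilt, because no effect size, SD or endpoint is given.

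**Counts.** Assessments: 1 + 12/2 = 7. A baseline-to-one-visit comparison uses 2 of 7 (29%). With 41 completers that is 41 × 2 = 82 of 48 × 7 = 336 scheduled scores (24%).

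**Multiplicity on the other reading.** Six tests at 0.05: 1 − 0.95^6 = 0.265. This assumes independent tests; correlated visits give less.

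**Power. Assumptions, not in the documents:** 24 per arm; 15% dropout, 3% after each of the first five post-baseline visits; random intercept (variance a), random slope (variance b, time scaled 0 at baseline to 1 at cycle 12) and visit noise (variance e). Completers per arm: n = 0.85 × 24 = 20.4. Variance of the cycle-12 arm difference:

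- change score, completers: 2(b + 2e)/n
- end score, completers: 2(a + b + e)/n
- ANCOVA, completers: 2[(a + b + e) − a²/(a + e)]/n
- repeated-measures model, visit as a category, all scores: generalised least squares with a common baseline mean

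Power with the reference test set at 80%: Φ(2.802 × √(V_ref/V) − 1.960).

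Example, (a, b, e) = (0.5, 1, 0.5): change 2 × 2/20.4 = 0.1961; ANCOVA 2 × 1.75/20.4 = 0.1716; model 0.1617. ANCOVA power = Φ(2.802 × 1.069 − 1.960) = 85.0%. Model power = Φ(2.802 × 1.101 − 1.960) = 87.0%.

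| a, b, e | ANCOVA (change score = 80%) | Model (change score = 80%) | Model (end score = 80%) | Model (ANCOVA = 80%) |
|---|---|---|---|---|
| 0.3, 1, 0.5 | 86.2 | 88.0 | 84.5 | 82.2 |
| 0.3, 1, 1 | 90.1 | 91.1 | 82.5 | 81.4 |
| 0.5, 0.5, 0.5 | 86.6 | 88.1 | 88.1 | 81.8 |
| 0.5, 1, 0.25 | 82.2 | 85.0 | 89.9 | 83.0 |
| 0.5, 1, 0.5 | 85.0 | 87.0 | 87.0 | 82.3 |
| 0.5, 2, 0.5 | 83.3 | 86.0 | 86.0 | 82.9 |

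Baseline adjustment supplies more than half of the gain over the change score in five of the six settings. The exception is (0.5, 1, 0.25), where it supplies 2.2 of 5.0 points.

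**Second check, other covariances.** With SD 1 at every visit and compound-symmetric (0.3-0.7) or AR(1) (0.5-0.9) correlation, the model's variance at the last visit is about 18-50% below the change score, but only about 1-5% below ANCOVA.

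**Linear arm-by-cycle model.** If the arm difference grows linearly, power is 89-97% (change score = 80%) or 87-91% (ANCOVA = 80%). If it appears only after cycle 6 and then rises to cycle 12, the linear model understates the cycle-12 difference by 10-21% and has 73-81% power against ANCOVA's 80%.

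**The case against.** A reader might infer that five of the seven scores are certain to be discarded, or that the named tests cannot use more than two time points. The documents do not support either. The analysis section names no visit, so t-tests at every visit are possible. An unpaired t-test on a per-patient slope, area under the curve or mean change would use all the scores. What is documented is that the analysis is left open.

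The loss of early leavers is also not due to the choice of test alone. Section D already removes them, so changing the test without that rule would not bring them back.

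It is also fair to say that repeated measures are not the main source of the gain. ANCOVA on two visits already gets most of it in most settings, and the extra visits add only 1-3 points. The larger figures for a linear model depend on the effect growing linearly. The Introduction says that neuropathy worsens with repeated cycles, which does not establish a linear difference between arms.

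Finally, a prespecified two-time-point t-test is valid, and no stated figure in the plan is shown to be wrong. All of this stands, and it limits the point to efficiency and specification. It does not remove the point: the plan names no ANCOVA and no summary measure, and leaves the choice of visit open.

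**Conclusion.** The point holds as a recommended improvement, not as an error that invalidates the trial. Ntx-12 is a primary outcome with seven scheduled scores, no stated time point, and only unadjusted tests named for it.

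Where a completers' change-score t-test has 80% power, a baseline-adjusted repeated-measures model with visit as a category has about 85-91%. Where a completers' end-score t-test has 80%, it has about 83-90%. ANCOVA alone accounts for 82-90% in the first comparison. The model's further contributions are 1-3 points of power, use of partial data from leavers, and one prespecified estimate in place of up to six tests.

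These figures rest on assumed variances and dropout, and on covariances treated as known, which slightly flatters the model at this sample size. The 89-97% obtainable from a linear trend should not be taken as the expected benefit, because it disappears if the effect comes late.

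**What to change.** For Ntx-12, and likewise for BPI-SF worst pain:

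1. State that the target is the arm difference at cycle 12, reported with a 95% CI.
2. Estimate it from one mixed model for repeated measures: baseline score as a covariate, visit as a category, arm and arm-by-visit, using every score collected from all allocated patients. The MIXED procedure in the SPSS 26 package already named can fit it. Entering baseline as a covariate does not force equal baseline means, which is prudent given allocation by day of admission.
3. State in section D that patients who stop tablets or miss a meeting stay in this analysis with the scores they have. This concerns which data are analysed, not treatment.
4. Keep a linear arm-by-cycle model as a secondary analysis only.
5. If residuals are clearly skewed, add a rank-based, baseline-adjusted comparison at cycle 12 as a sensitivity analysis.

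The cost is a few lines in the endpoint and analysis sections and one sentence in section D, written before outcome data are analysed. No new patients, visits or software are needed. The downsides are a somewhat more complex analysis at about 20-24 patients per arm and a missing-at-random assumption for leavers. A patient with no post-baseline score still adds nothing.

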### **B. Blood sample collection and biochemical assessment**

Before starting the first chemotherapy cycle (baseline) and after the last chemotherapy cycle, 5 ml of venous blood will be withdrawn by antecubital venipuncture from each participant between 8:30 and 10:30 am into plain test tube and centrifuged at 3000 rpm for 10 min. The separated sera will be frozen at  $-80^{\circ}\text{C}$  until analysis of the biological parameters which include:

- Malondialdehyde (MDA) as oxidative stress marker (colorimetry).
- Tumor necrosis factor alfa (TNF- $\alpha$ ) as pro inflammatory marker (ELISA).
- Neurotensin (NT) as a potential marker for neuropathic pain (ELISA).
- Citrulline as a biomarker for mucositis (ELISA).

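### The rank test named for within-patient comparisons ignores pairing (minor error), and the between-arm analysis of Ntx-12 fixes neither visit nor contrast and, as for the biomarkers, does not adjust for baseline (cheap improvement)

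*Combined protocol and SAP*

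**What the plan says.** The Statistical analysis section gives one bullet to each type of data.

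- **Parametric data:** paired and unpaired t-tests are used "to compare the means within the same group and to compare the means of the two groups respectively". The pairing is handled correctly.
- **Non-parametric data:** these are "analyzed using Mann Whitney U test to compare the means within the same group", and the same test is also named for comparisons between groups. No paired rank test is named anywhere.

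The data compared within a group are paired. Serum markers are taken from each participant "Before starting the first chemotherapy cycle (baseline) and after the last chemotherapy cycle". Ntx-12 is scored "at baseline and by the end of every two chemotherapy cycles", which over 12 cycles gives up to six post-baseline scores per patient.

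The endpoints section makes "the variation of 12-item neurotoxicity questionnaire (Ntx-12) total score" part of the primary endpoint. For the markers it states: "The secondary endpoint is the change in the serum concentrations of the measured biological markers". The analysis section names only unadjusted two-group tests. It does not say which quantity enters them, and it names no visit for Ntx-12.

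**The concern.** There are two separate matters.

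**The within-arm rank test.** Mann-Whitney U treats the baseline and follow-up values as two unrelated samples, so its actual error rate is not the nominal 5%. The direction depends on the data. With positive correlation and similar spread, real changes are missed. With a much tighter baseline and low correlation, or with negative correlation, there are too many false positives.

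**The between-arm analysis.** Ntx-12 is a primary endpoint, yet several analyses of it fit the text: any of six visits, and either change or final value. That leaves the choice open until data are in hand. For the same true effect and the same patients, power also differs between those choices. ANCOVA, which compares follow-up values with the baseline value as covariate, is close to the better of the two or above it, without anyone having to guess the correlation.

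**Working it through.** **Inputs from the protocol.** 48 patients enrolled, 24 per arm; 41 patients said to be sufficient; 5% significance (two-sided assumed), 80% power, 15% attrition. **Assumed, not in the protocol:** the correlation r between baseline and follow-up, the ratio k of baseline SD to follow-up SD, and the size of shift.

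**The plan's own figure.** 41 × 1.15 = 47.15, rounded up to 48; 41 / 0.85 = 48.2. The 48 is reproduced and is not in dispute. The 41 cannot be rederived, because no effect size, SD, endpoint or test is given.

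**1. Within-arm test.** Simulation with 10,000 datasets per setting and p ≤ 0.05. The first table uses skewed (lognormal) data with equal spread and n=20; power is for a shift of 0.6 SD on the log scale.

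| r | Type I, Mann-Whitney | Type I, signed-rank | Power, Mann-Whitney | Power, signed-rank |
|---|---|---|---|---|
| 0.3 | 2.3% | 5.0% | 42% | 49% |
| 0.5 | 0.8% | 5.0% | 43% | 63% |
| 0.7 | 0.1% | 4.8% | 41% | 83% |

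At n=24 the pattern is the same: Mann-Whitney power 51-52%, signed-rank 58-90%.

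Baseline SD one quarter of follow-up SD (k=0.25), normal or log scale, n=20:

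| r | Type I, Mann-Whitney | Type I, signed-rank | Power, Mann-Whitney | Power, signed-rank |
|---|---|---|---|---|
| 0.1 | 6.9% | 5.0% | 68% | 70% |
| 0.3 | 5.6% | 4.5% | 69% | 74% |
| 0.5 | 5.3% | 5.1% | 68% | 77% |

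With r = -0.3 and equal spread, Mann-Whitney type I error is 8.0-8.7%.

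**2. Between-arm analysis.** Take 21 v 20 patients and follow-up SD 1. Variances, each times (1/21 + 1/20):

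- final value: 1
- change score: 1 + k² - 2rk, which is 2(1 - r) when k = 1
- ANCOVA: (1 - r²)(1 + 1/37), where 1/37 = 2.7% is the cost of estimating the slope

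Equal spread:

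| r | Change | ANCOVA | Reduction v change | Reduction v final |
|---|---|---|---|---|
| 0.3 | 1.40 | 0.935 | 33% | 7% |
| 0.5 | 1.00 | 0.770 | 23% | 23% |
| 0.7 | 0.60 | 0.524 | 13% | 48% |

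In patients, 41 / (1 - reduction) means that 41 analysed by ANCOVA act like 61, 53 and 47 analysed by change scores.

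Low baseline spread (a minus sign is a loss):

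| k | r | Change | ANCOVA | ANCOVA v change | ANCOVA v final |
|---|---|---|---|---|---|
| 0.25 | 0.1 | 1.0125 | 1.017 | -0.4% | -1.7% |
| 0.25 | 0.3 | 0.9125 | 0.935 | -2.4% | +6.5% |
| 0.25 | 0.5 | 0.8125 | 0.770 | +5.2% | +23.0% |
| 0.50 | 0.1 | 1.15 | 1.017 | +11.6% | -1.7% |
| 0.50 | 0.3 | 0.95 | 0.935 | +1.6% | +6.5% |
| 0.50 | 0.5 | 0.75 | 0.770 | -2.7% | +23.0% |

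**Illustrative power.** An unpaired t-test with 21 v 20 evaluable patients has 80% power at 0.898 SD. If the 41 already include 15% attrition, as the sample size section also suggests, about 41 × 0.85 = 35 are evaluable and the figure is about 0.98 SD. At 0.9 SD with 21 v 20, equal spread and r = 0.3/0.5/0.7, power is 80%/80%/80% for final values, 66%/80%/95% for change scores and 83%/89%/97% for ANCOVA.

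**The case against.** The strongest reply is about weight. The wrong test touches only within-arm comparisons of data judged non-normal, and these do not estimate the treatment effect. Between arms, Mann-Whitney U and the unpaired t-test are legitimate, and preferring ANCOVA is a matter of efficiency. All of this stands, and it is why the first part is minor and the second an improvement.

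Four stronger readings might be inferred and are not supported:

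- **That the protocol nowhere says whether change or final values are compared.** The endpoints section does name change for the serum markers, and their two sampling times are fixed. The gap in visit and contrast is real for Ntx-12, where variation settles neither.
- **That the equal-spread figures describe Ntx-12.** The exclusion criteria remove patients with pre-existing neuropathy, so baseline Ntx-12 probably varies little. The low-spread tables are the better guide, and there the harm is small.
- **That the plan was powered for 0.9 SD.** It states only that "a total sample size of 41 patients in both arms will be sufficient to detect the effect". The figure depends on 41 being evaluable and on a t-test having been intended.
- **That baseline adjustment would rescue the comparison.** Patients are allocated "according to the days of hospital admission into two groups". ANCOVA does not repair that.

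A fair point against the remedy is that signed-rank has its own limits. On raw skewed values with equal medians but unequal spread, it rejects about 8-10% of the time at n=20, against 4.5-5.1% on the log scale. The log step answers this for the markers but not for within-arm Ntx-12, which is one more reason to treat those tests as descriptive.

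**Conclusion.** Both parts hold, at modest weight.

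1. **Wrong as written, minor.** Mann-Whitney U is the wrong test for the paired values. With equal spread and assumed r of 0.3-0.7, type I error is about 2% to 0.1%, and power at n=20 is 41-43% against 49-83%. With a much tighter baseline and positive r, type I error is about 5-7% and the power loss is small. No treatment comparison is invalidated.
2. **Cheap improvement.** For Ntx-12 neither visit nor contrast is prespecified, and no between-arm analysis of Ntx-12 or the markers adjusts for baseline. Under equal spread, ANCOVA reduces variance by 13-33% against change scores and 7-48% against final values. For Ntx-12, expect between about a 3% loss and a 12% gain against change scores.

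The error in the first part is plain from the text. The sizes rest on assumed correlations, spreads and shift, and the power figures on an illustrative effect. Unadjusted between-arm tests remain valid under proper randomisation. The grade ≥2 neuropathy endpoint is not affected.

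**What to change.** In the Statistical analysis section:

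- Name the Wilcoxon signed-rank test for within-arm comparisons of non-normal data, on the log scale for the serum markers. Keep Mann-Whitney U for between-arm comparisons only. Label all within-arm tests descriptive.
- Compare Ntx-12 total score at the end of cycle 12, and each marker after the last cycle, between arms by ANCOVA with the baseline value as covariate. Report the adjusted difference (a ratio for log-scale markers) with a 95% CI.
- Use the log scale for all markers by prior decision, not by looking at the data.
- For Ntx-12, always report a rank-based ANCOVA as a fixed sensitivity analysis, with no switch driven by a normality test.

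The cost is a few lines of text, with no extra data, visits or patients. The drawbacks are small: possibly up to about 3% lost precision for Ntx-12, marker results expressed as ratios, and a rule needed for undetectable values. Ntx-12 is bounded, but in simulated bounded scores ANCOVA kept type I error at 4.7-5.1% and the rank-based version at 4.8-5.3%.

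Naming one visit also calls for a stated rule on how patients without a cycle 12 score enter the analysis. ANCOVA does not supply one. A mixed model over all Ntx-12 visits is an alternative, provided that it is fixed in advance and the cycle 12 contrast is named. No change to the analyses of grade ≥2 neuropathy or mucositis grade is proposed here.
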